6.7 BASELINE, TIME WINDOWS AND CALCULATED VISITS

Measurements reported with date and time and taken prior to start of administration of trial treatment will be considered pre-treatment values. Measurements reported with a date only (and no time) and taken on the day of first administration of trial treatment will also be considered pre-treatment values. These pre-treatment values will be assigned to visits according to the nominal visit number as recorded on the eCRF or as provided by the laboratory.

Baseline, unless otherwise specified, is defined as the last measurement collected prior to the start of administration of the trial treatment.

For the baseline defined in efficacy endpoints like “change from baseline” or “compared to baseline”, unless otherwise specified, is defined as the last measurement before initiation of treatment (cf. [Section 5](#)).

Baseline for time to event endpoints, is defined as the last measurement collected prior to the start of administration of the trial treatment in the current extension trial 1368-0067.

For analysis of anti-drug antibodies (ADA), 2 different baselines will be used for the clinical trial report (CTR). For the analysis of ADA impact on pharmacokinetic (PK), the entire course of treatment is to be considered and assessments prior to initial trial of the parent trial (1368-0052) is considered baseline. Details will be discussed on the trial CTR.

For the analysis of ADA impact on safety and efficacy endpoints, baseline is defined as the first evaluable sample collected prior to treatment administration at baseline of this trial 0067.

Measurements taken after start of administration of trial treatment will be considered either on- or off-treatment values based on the definition in [Section 6.1](#), and will be assigned to visits for statistical analysis, if applicable, as defined below.

Analysis of AE data, potentially clinically significant abnormal laboratory values, concomitant medication or non-drug therapies, as well as use of rescue therapy will not be based on visits. Frequency tables for these data will be using on-treatment data and categorized based on their occurring/starting dates. Therefore, no assignment to time windows will be necessary for such data.

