The derivation of the last value, minimum value and maximum value of laboratory and vital signs data will consider all on-treatment values (whether or not selected in any time window; see [Table 6.1: 1](#) for definition of the on-treatment period) within the period of interest; these will be derived for analysis of laboratory and vital signs data.

All other safety, efficacy and biomarker measurements will be assigned to visits based on extended time windows around the planned visit dates, defined relative to the day of first trial treatment (which is scheduled for Visit 2). These extended time windows are defined in [Table 6.7: 1](#), [Table 6.7:2](#), [Table 6.7:3](#).

Proprietary confidential information © 2024 Boehringer Ingelheim International GmbH or one or more of its affiliated companies.

Table 6.7: 1 Time windows for assignment of vital signs to visits for statistical analysis.

Visit number	Visit label	Planned day	Time window [day]				
			Window (per CTP)	Start (per CTP)	End (per CTP)	Start (extended)	End (extended)
1	Week0	Day1	n/a	1 ^A	1	1 ^A	1
2	Week [redacted]	Day [redacted]	+2	[redacted]			
3	Week [redacted]	Day [redacted]	+2				
4	Week [redacted]	Day [redacted]	+2				
5	Week [redacted]	Day [redacted]	+2				
6	Week [redacted]	Day [redacted]	+2				
7	Week [redacted]	Day [redacted]	+2				
8	Week [redacted]	Day [redacted]	+3				
...				
53	Week [redacted] EoT	Da [redacted]	+3	[redacted]			
54	Week [redacted] (FUP1)	Da [redacted]	+3				
55	Week [redacted] (EOS)	Da [redacted]	+10				

For patients who discontinue the treatment early and are not willing to follow the whole visit schedule:
- EOS LD^B +112 - - -

All days are counted relative to the day of first treatment of current study, which is defined as Day 1.

* For the patients who enter OLE trial, V1 is strongly recommended to be performed during the EOT of the preceding parent trial.

^A Note that measurements made at Day 1 and assigned to the on-treatment period (because mistakenly made after start of trial treatment) via assessment on date & time (i.e. safety laboratory) will not be assigned to Day 1. Such data will be listed only.

^BLD= Last dose.

Proprietary confidential information © 2024 Boehringer Ingelheim International GmbH or one or more of its affiliated companies.

Table 6.7: 2 Time windows for assignment of DLQI, PGI-S, PGI-C, HiSQoL, Pain NRS safety lab, and biomarker to visits for statistical analysis

Visit number	Visit label	Planned day	Time window [day]								

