			Window (per CTP)	Start (per CTP)	End (per CTP)	Start (extended)	End (extended)				
1	Week0	Day1	n/a	1 ^A	1	1 ^A	22				
3	Week [redacted]	Day [redacted]	+2	[redacted]							
5	Week [redacted]	Day [redacted]	+2								
7	Week [redacted]	Day [redacted]	+2								
8	Week [redacted]	Day [redacted]	+3								
10	Week [redacted]	Day [redacted]	+3								
12	Week [redacted]	Day [redacted]	+3								
14	Week [redacted]	Day [redacted]	+3								
16	Week [redacted]	Day [redacted]	+3								
18	Week [redacted]	Day [redacted]	+3								
20	Week [redacted]	Day [redacted]	+3								
22	Week [redacted]	Day [redacted]	+3								
24	Week [redacted]	Day [redacted]	+3								
...					Midpoint of planned days between current visit and next visit			
52	Week [redacted]	Day [redacted]	+3								
53	Week [redacted] EoT	Day [redacted]	+3	[redacted]							
54	Week [redacted] (FUP1)	Day [redacted]	+3								
55	Week [redacted] (EOS)	Day [redacted]	+10								
For patients who discontinue the treatment early and are not willing to follow the whole visit schedule:											
-	EOS	LD ^B +112	-	-	-	-	-				

All days are counted relative to the day of first treatment of current study, which is defined as Day 1.

* For the patients who enter OLE trial, V1 is strongly recommended to be performed during the EOT of the preceding parent trial.

^A Note that measurements made at Day 1 and assigned to the on-treatment period (because mistakenly made after start of trial treatment) via assessment on date & time (i.e. safety laboratory) will not be assigned to Day 1. Such data will be listed only.

^BLD= Last dose.

Proprietary confidential information © 2024 Boehringer Ingelheim International GmbH or one or more of its affiliated companies.

Table 6.7: 3 Time windows for assignment of all the other efficacy assessments except those mentioned in [Table 6.7: 2](#) to visits for statistical analysis.

Visit number	Visit label	Planned day	Time window [day]				
			Window (per CTP)	Start (per CTP)	End (per CTP)	Start (extended)	End (extended)
1	Week0	Day1	n/a	1 ^A	1	1 ^A	1
2	Week						
3	Week						
4							

For patients who discontinue the treatment early and are not willing to follow the whole visit schedule:

- EOS LD^B +112 - - -

All days are counted relative to the day of first treatment of current study, which is defined as Day 1.

* For the patients who enter OLE trial, V1 is strongly recommended to be performed during the EOT of the preceding parent trial.

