^A Note that measurements made at Day 1 and assigned to the on-treatment period (because mistakenly made after start of trial treatment) via assessment on date & time (i.e. safety laboratory) will not be assigned to Day 1. Such data will be listed only.

^BLD= Last dose.

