7.8.2 Laboratory data

The analyses of laboratory data will be descriptive in nature and will be based on BI standards [\(12\)](#). Note that data from the central Laboratory will be used for all displays described below, unless otherwise specified.

For continuous safety laboratory parameters, normalized values will be derived. Normalisation means transformation to a standard unit and to a standard reference range. The process of normalisation, handling of repeat values at the same visit for by-visit displays, as well as standard analyses for safety laboratory data are described in the BI guidance for the Display and Analysis of Laboratory Data [\(12\)](#). All analyses considering multiple times of the ULN (as described below) will be based on standardized and not normalized values. For continuous safety laboratory parameters, differences to baseline will be calculated. For all outputs, the last assessment before the first treatment at Day 1 is chosen as the baseline value.

Only patients with at least one available post-baseline value will be included in the analysis of an individual laboratory parameter. All individual laboratory data will be listed. Values outside the reference range will be flagged.

For derivation of the last value, the minimum value, and the maximum value, all values during the entire treatment period will be considered under OR. These will be derived for analysis of laboratory, vital signs and local tolerability data. For identification of potentially clinically significant abnormal laboratory values, all values during entire treatment period will also be considered under OR.

Descriptive statistics of laboratory values over time and for the difference from baseline on-treatment (see [Section 6.7](#)) will be based upon normalized values and provided by visit (including follow up) under OC-IR, including summaries of the last value on-treatment, the minimum value on-treatment, and the maximum value on-treatment. Graphical displays via box plots will be produced for the change from baseline, over time, for each continuous laboratory endpoint.

Laboratory values will be compared to their reference ranges; shift tables will be provided for the number of patients with a specific RCTC grade at baseline versus the grade at the last measurement on treatment, as well as the worst grade on treatment. These analyses will be based on standardized laboratory values.

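### SAP Table 6.7: 2 runs the extended Week 0 window to Day 22, so off-schedule post-dose values would be labelled Week 0 in by-visit displays

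*SAP*

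**What the plan says.** SAP Section 6.7 assigns most post-dose data to visits by window: "All other safety, efficacy and biomarker measurements will be assigned to visits based on extended time windows around the planned visit dates". Three tables give the windows. Table 6.7: 1 covers vital signs. Table 6.7: 2 is titled "Time windows for assignment of DLQI, PGI-S, PGI-C, HiSQoL, Pain NRS safety lab, and biomarker to visits for statistical analysis". Table 6.7: 3 covers the remaining efficacy assessments.

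In Table 6.7: 2 the Week 0 row is "Week0 Day1 n/a 1 ^A 1 1 ^A 22". Under the column headers, this is a protocol window of Day 1 to Day 1 and an extended window of Day 1 to Day 22. In both other tables the row is "Week0 Day1 n/a 1 ^A 1 1 ^A 1". The day count is the same throughout: "All days are counted relative to the day of first treatment of current study, which is defined as Day 1". Footnote A says that timed values taken on Day 1 after dosing began "will not be assigned to Day 1. Such data will be listed only".

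Baseline is defined separately. Section 6.7 states: "Baseline, unless otherwise specified, is defined as the last measurement collected prior to the start of administration of the trial treatment". For laboratory outputs Section 7.8.2 adds that "the last assessment before the first treatment at Day 1 is chosen as the baseline value". Section 6.7 also places pre-treatment values by the nominal visit number on the eCRF or from the laboratory, not by window.

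**The concern.** Pre-treatment values never pass through the windows, so Days 2 to 22 of the Week 0 row have only one possible use: to label on-treatment values as Week 0. That conflicts with the two companion tables and with footnote A. A laboratory value drawn a few hours after the first dose is kept out of Week 0, yet one drawn on Day 20 is let in.

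What is at stake is the by-visit display. SAP Section 7.8.2 plans descriptive laboratory statistics by visit and box plots over time, and Section 7.6.1 plans questionnaire summaries by visit. Pain NRS also feeds the NRS30 secondary endpoint. A programmer who follows the table would place early post-dose values under the visit that readers take as pre-treatment, and those values would be absent from the first post-baseline visit.

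**Working it through.** **Inputs**
- Extended Week 0 window: Days 1 to 22 in Table 6.7: 2; Day 1 only in Tables 6.7: 1 and 6.7: 3.
- Visit rows in Table 6.7: 2: Visits 1, 3, 5, 7, 8, 10 and so on. The planned days are redacted.
- The rule visible in that table for later window ends: the midpoint between the planned days of the current and next visit.
- Visits 8 to 52 are two weeks apart, starting at W14 (protocol, second flow chart). The first flow chart has seven visits and is titled up to W12. Visit 3 has a window of ±2 days.

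**1. Post-dose days admitted to Week 0.** 22 − 1 = 21 days (Days 2 to 22).

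**2. Visit schedule.** With Visit 8 at W14, Visit 52 is at 14 + 2 × (52 − 8) = W102. EoT two weeks later is W104, which fits the roughly two years of treatment in protocol Section 6.2.3. Carrying the two-week spacing back puts Visit 7 at W12, which fits the first chart's title, Visit 3 at W4 and Visit 2 at W2. With day = 7 × week + 1, Visit 2 is Day 15 and Visit 3 is Day 29 (Days 27 to 31 with its window).

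**3. Can the midpoint rule reproduce Day 22?** The row after Visit 1 is Visit 3, and (1 + 29)/2 = Day 15. Day 22 is not reproduced. It is the midpoint of Visits 2 and 3: (15 + 29)/2 = 22. That would fit a Visit 2 row having been dropped and its end date carried into Week 0, but this is inference.

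**4. Alternative schedule.** The first flow chart prints its columns as W0 to W6. Taken literally, Visit 3 is Day 15 and Visit 5 is Day 29. The Visit 1 to Visit 3 midpoint is then (1 + 15)/2 = Day 8, so Day 22 is again not reproduced for Week 0. It would be the Visit 3 to Visit 5 midpoint, (15 + 29)/2 = 22. On this reading Visit 3 (Days 13 to 17) lies inside the Week 0 window. But a chart ending at W6 does not reach W12, and it leaves 14 − 6 = 8 weeks before Visit 8.

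**5. What falls in Days 2 to 22 on the two-weekly schedule.** Safety laboratory tests, pain NRS, questionnaires and biomarker samples are planned at Visits 1, 3, 5 and 7. The earliest on-schedule Visit 3 is Day 27, after Day 22. What remains:
- unscheduled visits for laboratory re-testing or AE monitoring (protocol Section 6.1);
- an EoT visit for very early discontinuation;
- the two-week follow-up visit of a patient dosed only on Day 1 (1 + 14 = Day 15).

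**6. What does not depend on the window**

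| Output | SAP place | Basis |
|---|---|---|
| Baseline | 5, 6.7, 7.8.2 | last pre-dose value; for efficacy in prior-spesolimab patients, the parent-trial baseline |
| Laboratory minimum, maximum, last | 6.7, 7.8.2 | all on-treatment values |
| Potentially clinically significant abnormalities | 6.7, 7.8.2 | not visit-based |
| Worst RCTC grade, eDISH peaks | 7.8.2 | on-treatment values, not visit summaries |

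**The case against.** The strongest reply is that the slip does little harm. This is a descriptive trial without hypothesis testing. A raised liver enzyme on Day 5 would still reach the maximum value, the worst grade, the abnormality tables, the eDISH plot and the listings. That stands, and it limits the point to by-visit displays.

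A reader might infer three stronger things that the documents do not support:
- **Post-dose values corrupt or displace baseline.** Baseline is fixed by pre-dose timing. Which record is shown when laboratory values repeat at one visit is left to a sponsor guidance that is cited but not reproduced, so displacement of the Week 0 record cannot be shown either.
- **The whole Visit 3 collection falls into Week 0.** This needs the W0 to W6 column labels to be right. They do not fit the chart's own title or the W14 start of the next chart.
- **Early safety signals would be lost.** The analyses meant to detect them do not use the windows.

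It can also be said that the table is largely redacted and split in the text, so a reading fault in this cell cannot be excluded. That also stands, and the source should be checked before anything is changed. Against it, the row has as many entries as the table has column headers, so 22 reads naturally as the extended end.

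**Conclusion.** As printed, Table 6.7: 2 contradicts its companion tables and its own footnote, and it would label post-dose values from 21 days as Week 0. The consequence is small. On the two-weekly schedule only unscheduled or early-discontinuation laboratory, questionnaire and biomarker values are affected, and only where they appear in by-visit summaries. The number of such values cannot be estimated from the documents.

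This rests on three assumptions: that the printed 22 is what the source table says; that visits are two-weekly from Visit 1, since the planned days are redacted; and that Day 1 is the intended end, which is inferred from the other two tables and footnote A because no text states it for this table.

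**What to change.** Check the cell in the source table. If it reads 22, set the extended Week 0 end to Day 1, as in Tables 6.7: 1 and 6.7: 3. Then state how Days 2 to 22 are assigned. Either of two rules would do:
- **Midpoint rule.** Values from the Visit 1 to Visit 3 midpoint onward (Day 15 on the two-weekly schedule) go to the first post-baseline visit. Earlier values are listed only, and laboratory values still count in minimum, maximum and last. The cost is that early questionnaire and biomarker values appear in listings alone, because Section 6.7 derives those three summaries only for laboratory and vital signs data.
- **All to the first post-baseline visit.** Nothing leaves the by-visit tables. The cost is that a Day 2 value would be shown under a visit planned for Day 29, 27 days later.

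The Visit 3 window start must be aligned with the chosen rule. Its current limits are redacted, so this cannot be checked here. The work is one cell, one sentence and a matching programming check.

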7. PLANNED ANALYSIS

Final trial analysis is planned to be performed at the end of the study once all patients have completed the study (including any follow-up period) if applicable. As specified in CTP in Section 7.2.7, multiple interim analyses may be done over the 2-year conduct phase of this trial. The corresponding snapshot will be taken for the interim analysis and data only up to the cut-off will be included into the analysis.

First interim analysis up to Week [REDACTED]

The interim analysis is planned after all patients in current study finishing their Week [REDACTED] visit or early discontinued before the visit, and a snapshot will be performed. All data collected up to Week [REDACTED] dosing will be included in this interim analysis.

Final analysis

Final trial analysis will be performed once all patients have completed the trial; at that time point, a final database lock will be done.

General Remarks

The format of the listings and tables will follow the BI guideline "Standards for Reporting of Clinical Trials and Project Summaries" (9) and those generated for PK will follow BI guideline "Standards and processes for analyses performed within Clinical Pharmacokinetics/Pharmacodynamics" (11).

The individual values of all patients will be listed, including those collected during the off-treatment period. Listings will generally be sorted by country, centre number, patient number and visit (if visit is applicable in the respective listing). AE listings will be sorted by assigned treatment (see [Section 7.8.1](#) below for details). The listings will be contained in Appendix 16.2 (SDL) of the CTR.

The following standard descriptive statistical parameters will be displayed in summary tables of continuous variables:

N:	number of non-missing observations
Mean:	arithmetic mean
SD:	standard deviation
Min:	minimum
Q1:	lower quartile
Median:	median
Q3:	upper quartile
Max:	maximum

For PK analyte concentrations, the following descriptive statistics will additionally be calculated: variables:

CV: arithmetic coefficient of variation
gMean: geometric mean
gCV: geometric coefficient of variation

The data format for descriptive statistics of concentrations will be identical with the data format of the respective concentrations.

Statistical parameters will be displayed to a defined number of decimal places as specified in the BI guideline "Standards for Reporting of Clinical Trials and Project Summaries" (9).

Tabulations of frequencies for categorical data will include all possible categories and will display the number of observations in a category as well as the percentage (%) relative to the respective treated patient set. Percentages will be rounded to one decimal place. The category missing will be displayed if and only if there are actual missing values. Percentages will be based on all patients in the respective patient set whether they have non-missing values or not unless there is another particular specification.

Disposition of the patient population participating in the trial will be summarised by presentation of the frequency of patients enrolled, treated, enrolled but not treated, who completed all doses of trial medication as planned, who completed the trial (EOS), who prematurely discontinued study treatment, by reason and who withdrew from the trial, by reason. Summary statistics of patients who did the dose modification at Week 12 and patients who discontinued due to no change observed at Week 24 after dose modification (according to Table 3.1: 1 in CTP) will be also displayed. The frequency of patients with iPDs will be presented; iPDs will be listed per patient.

To better illustrate the long-term disposition of entire maintenance treatment (cf. [Section 6.1](#)), a summary table regarding patient status over time will be added. The cumulative frequency of patients for the following categories will be displayed based on ■-week intervals:

- Ongoing on study medication, i.e., without early treatment discontinuation by the time point
 - Intake of rescue medication
 - Up-titrate the dose to ■
 - Any of the above
- Pre-maturely stopped study medication, i.e., discontinued study medication by the time point
 - Intake of rescue medication
 - Up-titrate the dose to ■
 - Any of the above
- Ongoing but not achieved the visit, if due to the cut-off of interim analysis
 - Intake of rescue medication
 - Up-titrate the dose to ■

- Any of the above

7.1 DEMOGRAPHIC AND OTHER BASELINE CHARACTERISTICS

Descriptive statistics will be presented for demographic parameters and baseline characteristics, based on the SAF.

Characteristics of the trial disease will be displayed for patients receiving at least 1 dose of study drug.

For the continuous variables described below, the following categories will be defined in [Table 7.1: 1](#), and presented according to the number and percentage of patients in each category:

Table 7.1: 1 Categories for summary of continuous variables

Variable	Categories
Age	<30 years 30 to <65 years ≥65 years
Body weight	≤60 kg >60 to ≤90 kg >90 kg
BMI	<25 kg/m ² 25 to <30 kg/m ² ≥30 kg/m ²
Time since first diagnosis	≤1 year >1 to ≤ 5 year >5 to ≤ 10 years >10 years

7.2 CONCOMITANT DISEASES AND MEDICATION

Only descriptive statistics are planned for this section of the report. Analyses of concomitant diseases and medication will be based on the SAF.

Concomitant diseases (i.e. baseline conditions) and concomitant non-drug therapies will be coded according to the most recent version of MedDRA. Concomitant medications will be coded according to the most recent version of the World Health Organisation – Drug Dictionary.

Concomitant diseases which are present at start of the study will be descriptively summarized.

A medication/non-drug therapy will be considered concomitant to treatment, if

- starting prior to day of first trial treatment OR on treatment in 1368-0052
- ongoing at the start of trial treatment or

Proprietary confidential information © 2024 Boehringer Ingelheim International GmbH or one or more of its affiliated companies.

- starting within the on-treatment period (see [Section 6.1](#) for a definition of study analysis phases).

Concomitant medication use (excluding rescue therapy) will be summarized with frequency and percentage of patients by preferred name. Summaries will be presented for

- starting prior to day of first trial treatment OR on treatment in 1368-0052
- concomitant medication starting any time during the on-treatment period (cf. [Section 6.1](#))

Concomitant use of non-drug therapies (excluding rescue therapy) taken any time during the on-treatment period (cf. [Section 6.1](#)) will be summarized with frequency and percentage. Summaries will be presented for

- starting prior to day of first trial treatment OR on treatment in 1368-0052
- concomitant non-drug therapies starting any time during the on-treatment period (cf. [Section 6.1](#)).

Use of rescue therapy will be summarized separately (see [Section 7.6.2](#)).

